1. PARTICIPANT CHARACTERISTICS AND RISK MITIGATION STRATEGIES

Admission into the study is open to men and women and to all racial and ethnic groups whose age is between 18-65. We will recruit a total of seventy-two cannabis use disordered participants from the community and randomize them to receive either active or sham rTMS.

a. General Inclusion / Exclusion Criteria

Inclusion Criteria:

- 1) Participants must be able to provide informed consent and function at an intellectual level sufficient to allow accurate completion of all assessment instruments.
- 2) Participants must be between the ages of 18 and 60.
- 3) Participants must meet DSM-5 criteria for at least moderate Cannabis Use Disorder, with use of at least 20 out of the last 28 days.
- 4) Participants must express a desire to reduce cannabis use or quit.
- 5) Participants must have a positive UDS for cannabis during their enrollment visit (confirming they are regular users).

Exclusion Criteria:

- 1) Participants must not be pregnant or breastfeeding.
- 2) Participants must not meet moderate or severe use disorder of any other substance with the exception of tobacco.
- 3) Participants must not be on any medications that have central nervous system effects.
- 4) Participants must not have a history of/or current psychotic disorder or bipolar disorder.
- 5) Participants must not have any other Axis I condition requiring current treatment and must have a HRSD₂₄ ≤10 indicating no clinically relevant depressive symptoms.
- 6) Participants must not have a history of Dementia or other cognitive impairment.
- 7) Participants must not have active suicidal ideation, or a suicide attempt within the past 90 days.
- 8) Participants must not have any contraindications to receiving rTMS or MRI (e.g. metal implanted above the head, history of seizure, any known brain lesion).
- 9) Participants must not have any unstable general medical conditions.

b. Recruitment and Informed Consent

We will use two primary recruitment methods to recruit from the community. We will work with trialfacts, a third-party study recruitment company, to advertise on social media platforms. We will perform a basic phone

screen for interested participants who are either referred from trialfacts, or are referred by Stanford clinicians. Those participants who meet basic inclusion/exclusion criteria based on the phone screen will be scheduled for either an in-person visit or an e-visit through Stanford's secure Zoom account. During the e-visit, participants will undergo a second level of screening with a research specialist. That meeting may occur directly after the phone screen, or immediately prior to the full enrollment visit. During that screening visit participants will be given a screening consent to review, and if interested will go through it with a qualified study team member. If understanding all of the risks of benefits of proceeding with a screening visit, the research staff will collect information in order to determine preliminary eligibility. Those participants who remain eligible after this level of screening will meet with one of the study physicians, most often the PD, who will review a full consent document. Participants completing this visit remotely will be asked to find a private location, and those coming in person will be given an informed consent document to review in a private office. The informed consent form includes a detailed description of the study procedures, along with statements regarding participants' rights to withdraw from the procedure at any time without consequences. After the participant reviews the informed consent document, one of the study physicians, most often the PD, will cover all of the key elements of informed consent with the participant and ensure they have an understanding of the RBA of participating in this study. Consent will be documented by the signature of the participant on the informed consent agreement, accompanied by the signature of the individual obtaining the consent. We will check the Stanford epic chart for all participants who have an MRN and will create an MRN for all those participants who do not.

c. Sources of Materials

Research material obtained from individual participants includes urine samples, fMRI-data, questionnaires, and interviews with study personnel. Additional information will be obtained from the Stanford Epic chart if the patient has one. All behavioral data will be directly input into REDCap which is a secure, password protected web-based data collection system. The only written research material will be the calendar from the Timeline Follow-Back. This paper record will be stored in a locked filing cabinet in an office at [name] that is locked when it is not in use. Urine samples will be delivered to the Stanford laboratory labeled only by participant ID, age, and gender. They will process the urine sample and send to the MUSC laboratory (contract submitted and approved), who will deliver results via secure email. MRI data will be kept in secure Stanford servers.

d. Potential Risks and Risk Mitigation Strategies:

Potential risks of rTMS: The use of high frequency rTMS has been FDA approved for the treatment of major depressive disorder since 2008. Our stimulation parameters (4000 pulses, 10Hz, 5-Seconds on 10-Seconds off) are nearly identical to the FDA approved protocol (3000 pulses, 10Hz, 4-Seconds On, 8-Seconds off), and have been used safely in many investigations including those in depression(25), pain(45), and addictions(46, 60). We chose to use the slightly longer train duration of 5-seconds rather than 4-seconds due to its demonstrated safety and efficacy in many trials including our preliminary single session trial with cannabis users. We chose to increase the number of pulses in each treatment from 3,000 to 4,000 pulses, as we wanted to ensure we gave an adequate dose of rTMS. The common clinical dose of rTMS in depression is 36 treatments with 3000 pulses per treatment, for a total of 108,000 pulses(23). We will deliver a total of 20 study-treatments with 4,000 pulses per treatment, for a total of 80,000 pulses. We subsequently will be giving a lower total dose to each participant than is commonly given to patients being treated for depression. We may deliver our twenty treatments in as few as two weeks which also differs from the standard FDA approved protocol (treatment may be accelerated). Accelerated treatment paradigms have been safely delivered in both depression(25-27, 61), and addictions (62, 63) populations without any clear adverse effect.

Risk of Seizure: The most serious risk associated with the use of rTMS is seizure. Since the adoption and widespread use of standard safety guidelines in 1997 (64), there have only been a few documented seizures. The risk of seizure has been estimated to be less than 1:30,000 treatments, (or less than 1:1000 courses of treatment), which is lower than the risk of seizure associated with pharmacologic antidepressants(65). The risk of seizure is related to the various stimulation parameters (intensity, frequency, train duration), location of

application, pre-existing risk of seizure, and substance/medication factors. In order to mitigate the risk of seizure we will carefully individualize the intensity of stimulus (by performing a resting motor threshold determination), treat using standard treatment protocols (used safely in other studies), and exclude potential participants at higher risk of seizure (those with a past history of seizures, those with known CNS lesions, those in withdrawal from alcohol or benzodiazepines etc). Neither cannabis use or withdrawal are known to increase the risk of seizure, and subsequently we do not believe concurrent use of cannabis, or early abstinence from regular cannabis use will result in any increased risk of seizure. In the very rare event rTMS causes a seizure, removing the coil is typically sufficient to stop the seizure, and there is no increased risk of subsequent seizures.

Risk of site discomfort and headache: Two relatively common risks associated with the use of rTMS include the risk of mild transient site discomfort during treatment (most patients), and the risk of post treatment headache (Approximately 5%). Both of these potential side effects are typically mild. In terms of mitigating site discomfort, we will slowly ramp up stimulation intensity during the first three sessions. In our experience both clinically and experimentally, ramping initial sessions results in improved tolerability of treatment. Additionally, due to the anti-pain effect of rTMS participants rapidly adjust to stimulation. In the unusual circumstance that a headache is caused by rTMS, over the counter analgesics are typically sufficient to alleviate the headaches, and we will forewarn participants of the possibility of headache and the effectiveness of over the counter analgesics.

Potential hearing loss: The discharge of the TMS coil generates a high-energy click that may cause cochlear damage. Humans exposed to rTMS have shown temporary increases in auditory threshold (especially at high frequencies) lasting at least 5 minutes and less than 4 hours. Foam earplugs can protect against these changes and will be worn during rTMS sessions.

Safety in the case of pregnancy: This protocol will exclude pregnant women. Pregnancy status will be confirmed during the baseline visit with a urine pregnancy test, and we will only include participants if they are willing to use an effective form of birth control.

Potential Risks of MRI: The risk from magnetic resonance imaging (MRI) is low. No radiation or x-rays are used in making pictures of the brain during MRI. Participants cannot have an MRI scan if they have metal in the skull, metal implants, a cardiac or brain pacemaker, or old metal fragments in the eye or retina. The major potential risks are primarily for those individuals who have metallic implants, or pacemakers. These individuals will be excluded from the study. Other potential hazards of MRI scanning include: collision hazards, noise, body temperature changes, helium, and nitrogen hazards. The MRI facility is tested regularly by internal and external safety monitoring teams. These risks are minimal, and within FDA guidelines. We will guard against scanning anyone with implanted metal by screening all potential participants thoroughly. Although the MRI scanner is open on both ends, some people become anxious when entering the MRI scanner due to the feeling of being enclosed. We will exclude those participants who report claustrophobia, and immediately remove participants undergoing scans if they feel uncomfortable. There is a theoretical risk of harm to an unborn child and consequently all women of child-bearing potential will be given a urine pregnancy test prior to the scanning procedures, and all women of childbearing age must be on a reliable form of contraception.

Potential risks of cue Induced craving paradigm: Drug cues are known to increase craving, and subsequently the use of a cannabis cue paradigm will likely temporarily increase craving for cannabis(49). We will mitigate the risk of increased craving in two ways. First, our cannabis cues will all be given while participants are closely monitored by study staff, eliminating the possibility of participants immediately going to use cannabis. Second, we will continually assess craving using the Marijuana Craving Questionnaire until participants are within 20% of baseline craving. We will ask them to stay until they have reached this threshold of craving in order to reduce the chances of them leaving the appointment and immediately using cannabis. Should participants have elevated craving beyond 1-hour post cue exposure we would have one of the study physicians meet with the patient and provide counseling to prevent possible excess use.

Risks of Motivational Enhancement Therapy (MET): Motivational enhancement therapy is well tolerated, and rarely associated with adverse effects (owing to its supportive, non-judgmental approach). Nonetheless, it is possible that participants will feel distressed while discussing sensitive topics. We mitigate this risk by having

a trained therapist deliver MET—most often the PD. The study-therapist will be trained on techniques to reduce any distress experienced by the participant.

Safety plan for suicidal or decompensated participants: Should any patient report suicidality on the Hamilton Depression scale, the MINI, or in any other manner, the PD or covering physician will evaluate the participant and make any appropriate referral.

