General Overview (Figure 3): The primary aims are to determine the efficacy of 20 sessions of DLPFC rTMS in decreasing cannabis cue-induced craving (Aim 1) and cue reactivity in a validated fMRI paradigm (Aim 2). The aims of the study will be accomplished by performing a double-blind, randomized, sham controlled clinical trial with two arms. Individuals with CUD will be

recruited from the community. All participants will receive a three-week behavioral intervention and adjunctively undergo a course of either *active* or *sham* rTMS during that time. Post-treatment

outcomes will be assessed at two- and four- weeks following completion of the rTMS course.

Screening: Participants will meet with study personnel either in person, or via Stanford Secure Zoom, and complete

assessments about substance use, psychiatric and medical history. Eligible participants will complete questionnaires and provide a urine sample for drug screening. For females, a pregnancy test will be done prior to the drug screen. Pregnant women will not be allowed to participate.

rTMS Sessions: rTMS will be delivered via a MagPro double blinded rTMS Research System (MagVenture, Denmark) with a Cool-B65 Butterfly Coil (a combined active and sham coil). We will use a standard resting motor threshold (rMT) determination to determine the TMS dose (42). Treatment will be delivered at 120% rMT. Each active rTMS study-treatment will consist of a total of 4000 pulses of 10Hz stimulation (5s-on,10s-off). Treatments will be delivered at the EEG coordinate for F3 (which approximates the left DLPFC), and will be found using the Beam-F3 method (43). This is a treatment paradigm that has been used extensively in other trials (25, 44-46). Sham sessions will be delivered using an electronic sham system consisting of a coil that mimics the appearance and sound of rTMS, combined with a TENS device which produces a small electric shock mimicking the feeling of active rTMS. This type of sham has been demonstrated to be indistinguishable from active rTMS, has been well tolerated in (21, 25), and successfully used in other clinical trials(47, 48).

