Behavioral Platform: We will use the three-session version of Brief Marijuana Dependence Counseling BMDC (51) for our behavioral platform, and will follow the protocol outlined in the manual published by NIDA (52). Briefly, we will generate personalized feedback reports (PFRs) by collecting the following measures: Marijuana Use Summary Sheet, Self-Efficacy Questionnaire, Marijuana Problem Scale, and Reasons for Quitting Questionnaire during the baseline visit. These PFRs are used by the clinician to facilitate discussion in the three MET sessions, which will occur most often at treatment visits 2, 4, and 10, regarding participants' frequency of cannabis use, concerns related to use, possible reasons for changing use, high risk use situations, and short and long-term goals related to reduction of use. To ensure our behavioral platform is delivered with fidelity, we will audio-tape sessions for review and fidelity ratings. The audiotapes will be reviewed and assessed for fidelity utilizing techniques developed in the Motivational Interviewing Assessment: Supervisory Tools for Enhancing Proficiency (MIASEP) manual (53).

[figure not shown]
Follow-up: There will be follow up visits 2-weeks and 4-weeks after treatment completion. Participants will be asked about cannabis use and urine drug tests will be performed.

Open label extension: Those participants not achieving abstinence following the four-week follow-up visit, who are interested, will be offered 20 additional treatments of rTMS in an open label fashion. Treatments will

Figure 4

Figure 5

Use of this paradigm elicits: Robust activation in reward regions including the medial prefrontal cortex and anterior cingulate in cannabis, compared to neutral, stimuli in heavy cannabis users.

be delivered in the same fashion as above, however only active treatment will be given (there will be no possibility of sham treatment). Craving, and other data may be collected in the same fashion as during the primary experiment.

Recruitment and Participant Population:

Recruitment: Participants will be recruited through media advertisements (such as Craigslist and facebook) using trialfacts, a professional study-recruitment agency. Ads will recruit heavy cannabis users who are interested in quitting. Participants will undergo a phone screen to ensure they meet basic eligibility criteria (See included phone screen).

Participant Population:

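### The risk section says every participant gets a lower total rTMS dose than a usual depression course, but an active-arm participant who completes the open-label extension can reach 160,000 pulses, 48% above that comparator

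*Combined protocol and SAP*

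**What the plan says.** The comparison is in the protocol's human-subjects part, under Potential Risks and Risk Mitigation Strategies, in the paragraph on the risks of rTMS. It gives the reference course first: "The common clinical dose of rTMS in depression is 36 treatments with 3000 pulses per treatment, for a total of 108,000 pulses(23"). The study course follows: "We will deliver a total of 20 study-treatments with 4,000 pulses per treatment, for a total of 80,000 pulses". From these two totals it concludes: "We subsequently will be giving a lower total dose to each participant than is commonly given to patients being treated for depression".

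The Open label extension paragraph in Research Design and Methods describes a second course. It is for "Those participants not achieving abstinence following the four-week follow-up visit, who are interested"; they "will be offered 20 additional treatments of rTMS in an open label fashion". Delivery is to match the main course, except that only active stimulation is given. The paragraph does not restrict the offer to participants who first received sham.

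The paragraphs that follow the dose comparison (seizure, discomfort and headache, hearing, pregnancy, MRI, cue exposure, behavioural therapy) do not mention the extension. The 2023 SAP compares adverse events by condition and site and does not mention it either.

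**The concern.** The cumulative comparison serves as reassurance. It comes directly after the protocol explains why it uses more pulses per treatment than the FDA-approved course (4,000 against 3,000). It is worded for every participant and for total dose, with no limit to the randomised phase, yet the same protocol provides a route by which some participants receive twice the number of treatments counted.

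What is at stake is the accuracy of a safety-exposure statement. The protocol goes on to call the balance of risk and benefit favourable for each individual participant. It also judges whether an adverse event is unexpected partly by what the current protocol describes. The participants with the highest possible exposure are those to whom the sentence does not apply. No endpoint, sample size or randomised comparison is affected.

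**Working it through.** **Inputs**
- Depression comparator: 36 treatments of 3,000 pulses (risk section).
- Randomised course: 20 treatments of 4,000 pulses (risk section). The rTMS Sessions paragraph agrees on the pulses: "Each active rTMS study-treatment will consist of a total of 4000 pulses of 10Hz stimulation (5s-on,10s-off").
- Extension: 20 further treatments, active only, delivered as in the main course, so 4,000 pulses each (Open label extension).

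**Formula:** total pulses = number of active treatments × pulses per treatment.

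**Step 1. Reproduce the plan's figures.**
- Comparator: 36 × 3,000 = 108,000, as stated.
- Randomised course: 20 × 4,000 = 80,000, as stated.
- Ratio: 80,000 / 108,000 = 0.741, or 25.9% below the comparator. The sentence is correct for this course.

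**Step 2. Add a completed extension, by original arm.**

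| Path | Active treatments | Active pulses | Against 108,000 |
|---|---|---|---|
| Active arm, no extension | 20 | 80,000 | 25.9% lower |
| Sham arm, full extension | 0 + 20 | 80,000 | 25.9% lower |
| Active arm, full extension | 20 + 20 | 160,000 | 48.1% higher |

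For the last row, 160,000 / 108,000 = 1.481, and the excess is 160,000 − 108,000 = 52,000 pulses.

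**Step 3. Find where the statement stops being true.**
- An active-arm participant starts the extension at 80,000 pulses.
- (108,000 − 80,000) / 4,000 = 7, so the comparator is equalled at the 7th extension treatment.
- At the 8th, the total is 28 × 4,000 = 112,000, which is 3.7% above it. Less than half of the extension is therefore enough.

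**The case against.** The strongest defence is scope. The sentence directly follows the count of 20 study-treatments, so it can be read as describing that course. The protocol sets the extension apart from its primary experiment, and the 48% compares two courses, at least four weeks apart, with one depression course. Much of this stands: both stated totals are right, there is no arithmetic error, and course against course the study dose is lower. But the sentence speaks of the total dose to each participant and carries no such limit, and nothing nearby tells the reader that a second course exists.

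A reader might infer several stronger points. The documents do not support them.

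- **Seizure risk above the quoted ceiling.** The protocol says: "The risk of seizure has been estimated to be less than 1:30,000 treatments, (or less than 1:1000 courses of treatment"). Scaling linearly, 40 / 30,000 = 1:750, which looks worse than 1:1000. But 40 treatments are two courses, and two courses at the per-course ceiling give 2/1000 = 1:500. The comparator itself scales to 36 / 30,000 = 1:833, also above 1:1000, so the two rounded upper bounds do not convert linearly. Cumulative pulses are not among the seizure risk factors that the protocol lists.
- **A concealed daily load.** Two treatments per treatment-day are stated in the Specific Aims and in the methods. The risk section says that a two-week schedule differs from the approved one and cites accelerated trials in support.
- **The only quantitative safety argument, or no risk statement covering the extension.** The seizure paragraph gives numerical rates, and the text on seizure, discomfort, headache and hearing is not limited to the first course.
- **Most of the active arm will reach 160,000 pulses.** If 10% to 40% of the active arm were abstinent, 36 × 0.90 = 32.4 down to 36 × 0.60 = 21.6 participants might be eligible. That is eligibility, not exposure: uptake is unknown and the extension carries no additional compensation. The 10% is a placebo rate from the sample-size section, defined there by a urine cut-off that the extension paragraph does not mention.
- **Consent or DSMB material is deficient.** The consent pages are not in the supplied text, and the protocol defers to a separate detailed monitoring plan. Their content needs checking and cannot be presumed wrong.

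**Conclusion.** The concern holds as an unscoped statement that conflicts with another part of the same protocol. For active-arm participants who accept and complete the extension, the total is up to 160,000 pulses, against 80,000 counted in the risk section and 108,000 for its comparator.

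This assumes that the extension uses 4,000 pulses per treatment, which follows from its matching the main course, and that all 40 treatments are given. The 160,000 is therefore a maximum; the documents do not allow an estimate of how many participants reach it. The contradiction needs only one active-arm participant to receive eight extension treatments.

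It would be worth correcting because it concerns safety exposure and is cheap to put right. It does not bear on the efficacy analysis. Nothing here says that either dose, or the extension itself, is right or wrong.

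**What to change.** - **Reconcile the two passages.** Limit the lower-total-dose sentence to the randomised 20-treatment course. Add the maximum cumulative exposure with the extension: 40 treatments and 160,000 pulses for a participant first assigned to active, and 80,000 active pulses for one first assigned to sham. State that the two courses are separated by the four-week follow-up.
- **Check consent and DSMB material.** Confirm that they describe the same maximum, and align them if they do not.
- **Report extension safety separately.** Tabulate adverse events in the extension apart from the randomised phase, by original arm or by cumulative exposure, with the number who entered and the treatments received.

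The 2023 SAP is written in the past tense, so treatment may be over. In that case the accurate exposure statement and the separate table can still go into the trial report. The cost is a few sentences, one extra table and a less favourable stated exposure. Sample size, endpoints and models are unchanged.
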